A "data not available" response will be available where appropriate for those record abstraction items for which data may be missing from patient records. This type of response will help reduce missing data and will document the overall gaps in record keeping.

A brief pilot test of the translated version of the abstraction form will be conducted in each country, and the abstraction form in one or more countries may be adjusted based on the results of this pilot.

A draft version of the medical record abstraction form is included with this document (Appendix 1).

Off-Label Use Definition

The definition of off-label use of MabThera will be based on the use for a non-oncology disease or medical condition other than RA and GPA/MPA covered by MabThera SPC.

In absence of labelled indications, potential off-label use could include, but is not limited to, the following conditions:

- Ankylosing spondylitis
- Psoriatic arthritis
- Undifferentiated spondyloarthritis
- Juvenile idiopathic arthritis
- SLE
- Systemic vasculitis

- Eosinophilic GPA
- Inflammatory myopathies
- Behçet disease
- Sjögren syndrome
- Nephrotic syndrome
- Glomerulonephritis
- Multiple sclerosis/neuromyelitis optica
- · Pemphigus vulgaris
- Polydermatomyositis
- · Mixed connective tissue disease

Patient Survey data

The patient questionnaire has been developed following standard survey methodological principles and will be cognitively tested with patients in each of the target countries. Modifications will be made to the questionnaire based on the results of testing, and some variations to the questionnaire are anticipated based on country-specific requirements.

The questionnaire will include an introductory section with questions to confirm eligibility. The majority of the questionnaire items will be closed ended, ensuring that the resulting data are easy to analyse and interpret. Closed-ended questions are generally more efficient than open-ended questions (or open-ended text fields) and more conducive to summarisation and statistical analyses.

The questionnaire will collect the following information (please refer to Appendix 1 for the draft questionnaire):

- Demographics (e.g., age, sex, ethnicity)
- Patient previous history of PML or other serious infectious diseases
- Whether the patient has received a previous treatment with MabThera, if so, number of prior infusions during the last 12 months
- Patient understanding or awareness of the following:

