 - Known and potential risks of infection associated with MabThera including the risk of PML
 - -Symptoms of infection, including PML, and what actions patients should take
 - -Who should not be treated with MabThera
 - -What medication information patients should tell their doctor
 - -Any other counselling received for the infections covered in the PAC
- Patient receipt and reading of the PAC

- -How often has the patient received the PAC?
- –Does the patient currently have a PAC?
- Has the patient received a package leaflet (i.e., PIL)? Does the patient currently have one?
- Patient receipt of additional safety-related information about MabThera
- Patient actions and any changes in behaviour triggered by the PAC (for example, if the patient consulted another physician following the first MabThera treatment or if the patient showed the card to a doctor other than one associated with the MabThera treatment).

Other descriptive information about the patient will be collected to enable stratification of results and facilitate comparison of study participants with the total sample of patients receiving MabThera at participating sites.

Patient Questionnaire Administration

The questionnaire will be completed after the patient arrives at the centre and before the start of the infusion to make sure the questionnaire is completed before any additional counselling regarding the content of the PAC is provided by the site. According to the responses to the feasibility evaluation, all sites considered this to be feasible considering their infusion and counselling practices.

The patient questionnaire will be self-administered (closed-ended questions with predefined answers) on a hard-copy form at the site. The questionnaire will be translated into each local language (English, French, German, Italian, and Spanish) and pretested. Although there are a number of advantages to using an electronic format for questionnaire administration, based on the results of the feasibility evaluation, paper data collection forms are the most efficient approach for this study given the centres' preferences, infrastructure, and the number of patients per centre. Written informed consent will be obtained from each patient prior to completion of this questionnaire.

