8.6 DATA ANALYSIS

Analysis of MabThera off-label use and evaluation of PAC knowledge and utilisation will be descriptive in nature and will entail the tabular display of summary statistics and the frequency distribution of item responses.

A detailed analysis plan describing methods of analysis and presentation, as well as table shells, will be developed prior to starting analysis of data. In addition to describing the analysis of off-label use, for the questionnaire data, the analysis plan will describe any planned comparisons of participants and non-participants. The analysis plan will also describe the following:

- Analysis of subgroups
- · Methods for handling missing data
- Level of statistical precision

All analyses will be performed using SAS 9.2 (or higher) statistical software (SAS Institute Inc., Cary, North Carolina, USA). Programs, logs, and output will be reviewed for accuracy according to relevant standard operating procedures.

The analysis of off-label use will be descriptive and will present MabThera utilisation by indication (RA, SLE/LN, other). Results will be evaluated by site characteristics, including country and geographic region within country, to ascertain any patterns of prescribing by specific indication. The main analysis will be to estimate (with 95% CIs)

^a With an average cluster size of 8 patients, correlation coefficients of 0.15 and 0.30 correspond with design effects of 2.05 and 3.1, respectively.

^b The percentage in this column does not need to represent only the percentage of correct responses; it can represent any percentage, for example percentage of abstractions that were identified as off-label use or percentage of abstractions that had systemic lupus erythematosus (SLE).

the proportion of off-label use among users of MabThera during the entire study period in the 5 European countries of interest. The proportion of each of the most common off-label use indications will be described among the entire off-label use group. In addition, an estimate of off-label usage will be determined amongst prevalent (i.e., repeat infusions) and incident (i.e., patients attending for their first MabThera infusion) patients to the extent that incident use can be accurately determined. Characteristics of patients meeting the definitions for both strict and broad on-label use will also be evaluated. The dosage of MabThera used by infusion will also be estimated in the on- and off-label groups.

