Exploratory analyses will be conducted to examine low awareness of key safety elements based on patients who read the PAC vs. those who did not; patients who were

infused in-office vs. infused at independent infusion centres; and incident MabThera patients (i.e. patients receiving their first course of MabThera) compared with patients who had received 2 or more courses.

Results of both components of the study will be examined to assess any implications for the MabThera communication and education activities, including the PAC, and for physicians and patients on the appropriate use of MabThera. If any findings suggest extensive off-label use or suboptimal patient knowledge of the PAC or patient-reported practice patterns, root cause analyses may be explored, as appropriate (e.g., additional exploratory analyses, follow-up discussions), with infusion centres that participated in the survey. Follow-up contact with infusion centres might examine differences in practices by site type. Results of the study and root cause analyses can be used as input into potential modifications to the MabThera communication and education activities, including the PAC programme.

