The questionnaire should take approximately 10 to 15 minutes to complete. Your responses will be kept confidential and will not be shared with your doctor or other health care professionals.

Please answer the following questions to confirm that you are eligible for this study.

S1.	Are you 18 years of age or older?
	□ Yes
	□ No (If no, please speak with your nurse or doctor to confirm your eligibility.)

Questionnaire

The purpose of the study is to learn more about patients' understanding of the important safety information related to MabThera (rituximab). As we are trying to find out your current understanding, please do not look at the MabThera patient alert card or other materials while answering the following questions. The information gathered from this study will help to improve communication about the safe use of MabThera (rituximab).

Note: For review purposes, an asterisk (*) indicates correct responses.

Q1.	Approximately when was your first infusion of MabThera (rituximab)? (Select the one answer that best applies to you.) ☐ This is my first infusion ☐ Less than 3 months ago ☐ Between 3 months and 9 months ago ☐ More than 9 months ago ☐ I don't know
Q2.	During the past 12 months, approximately how many times have you received MabThera (rituximab), which is always given by an IV (intravenous) infusion? 1 time 2 times 3 times 4 times I don't know
Q3.	Where do you get most of your information about MabThera (rituximab)? (Select the one most correct answer.) From my doctor who prescribed MabThera (rituximab) From another doctor at the infusion centre From the nurse at the infusion centre From my chemists/pharmacy¹ From a friend or family member (spouse, adult child) From my professional caregiver From the Internet Other, please specify:

¹ Use "chemists" for UK and "pharmacy" for other countries.

Risk Assessment

The following questions ask about the risks and side effects that patients could potentially experience when taking MabThera (rituximab). Please note these questions are just to learn more about your knowledge of these risks and not about your specific experiences while taking MabThera (rituximab).

Q4.	Has your doctor or other health care professional (e.g., a nurse) ever talked to you about the possible risks of receiving MabThera (rituximab)? ☐ Yes ☐ No ☐ I don't know
Q5.	Which of the following side effects can potentially happen in patients who are receiving MabThera (rituximab)? (Select all that apply.) Hair loss

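### Section 8.6 defines 'incident' as first infusion in one analysis and first course in another; neither draft form records courses, so the first-course contrast can only be approximated, and survey item Q2 has no answer for 0 or for more than 4 infusions.

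*Protocol*

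**What the plan says.** Section 8.6 (Data Analysis) plans an additional estimate of off-label use among prevalent patients, meaning those with repeat infusions, and among "incident (i.e., patients attending for their first MabThera infusion) patients to the extent that incident use can be accurately determined". Further on, the same section lists exploratory analyses of low awareness of key safety elements. One of them sets "incident MabThera patients (i.e. patients receiving their first course of MabThera) compared with patients who had received 2 or more courses".

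For the survey, section 8.3 (Variables) plans to collect this exposure history: "Whether the patient has received a previous treatment with MabThera, if so, number of prior infusions during the last 12 months". In the draft questionnaire (Appendix 1), Q1 asks when the first infusion took place. It offers "This is my first infusion", three time bands (under 3 months, 3 to 9 months, more than 9 months) and a don't-know option. Q2 begins "During the past 12 months, approximately how many times have you received" the drug, and its complete list of answers is "1 time 2 times 3 times 4 times I don't know". On timing, section 8.3 states: "The questionnaire will be completed after the patient arrives at the centre and before the start of the infusion".

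The draft abstraction form asks for the dates of the first and most recent infusions and for the number of infusions in the past 2 years. Its supplement for rheumatoid arthritis refers to a current treatment cycle but asks for neither its number nor its start date.

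**The concern.** There are two separate problems.

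The first is the definition. If a course has more than one infusion, a patient at the second infusion of a first course is prevalent in the off-label analysis and incident in the awareness analysis. The report would then carry two different groups under one name. The second definition also depends on a quantity, the course, that the protocol does not define and that no draft form collects. An analysis plan written later can choose a rule, but it cannot recover a variable that was never recorded.

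The second is the answer set of Q2. The questionnaire is filled in before the day's infusion, so some patients have a true count of zero and others may have had more than four. Neither group has a valid answer. Section 8.3 makes the count conditional on earlier treatment, but the draft Q2 has no skip for first-infusion patients, although later items such as Q14 and Q18 do have skips.

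At stake is whether the new-versus-experienced comparison of safety awareness means what its label says. Section 8.6 allows the study results to feed into changes to the alert card programme.

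**Working it through.** The plan gives no figure on this point, so there is none to reproduce. The check sets the definitions against the forms and then asks what Q1 and Q2 can settle.

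**Definitions.** Let L be the number of infusions in a course. The documents give no value; L = 1, 2 and 4 are assumptions for illustration only, and nothing here says what a course should be. A patient attending for infusion number 2 to L of a first course is prevalent under the first definition and incident under the second. That is L − 1 visits per patient: 0 if L = 1, 1 if L = 2, 3 if L = 4.

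**Items that could identify a course.**
- Questionnaire: Q1 (time since first infusion) and Q2 (times in the past 12 months). There is no course item.
- Abstraction form: first and most recent infusion dates and a 2-year count. There is no course number. Section 8.1.1 promises to capture repeated treatment intervals, but the draft form shows no field for them.
- Both together: section 8.6 plans to combine survey and records only for patients consenting to both, and only to group results by clinical condition.

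**What Q1 and Q2 settle.** Let N be the number of infusions before today and k the Q2 answer. With a fixed course length, today's infusion belongs to the first course if N < L, and otherwise to a later one.
- Q1 = first infusion: N = 0 whatever Q2 says.
- Q1 up to 9 months: all earlier infusions fall within 12 months, so N = k, or k − 1 if the patient counts today's infusion (with N at least 1).
- Q1 more than 9 months: N is at least the larger of k − 1 and 1, with no upper limit, because earlier infusions may lie outside the 12 months.

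In the table, F is first course, 2+ is a later course and ? is undetermined.

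| Q1 answer | L = 2: k = 1, 2, 3, 4 | L = 4: k = 1, 2, 3, 4 |
|---|---|---|
| first infusion | F, F, F, F | F, F, F, F |
| under 3 months | F, ?, 2+, 2+ | F, F, F, ? |
| 3 to 9 months | F, ?, 2+, 2+ | F, F, F, ? |
| more than 9 months | ?, ?, 2+, 2+ | ?, ?, ?, ? |

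Undetermined cells: L = 2 gives 1 + 1 + 2 = 4 of 16; L = 4 gives 1 + 1 + 4 = 6 of 16, and no cell is then certain to be a later course. With L = 1 all 16 are settled, because Q1 alone separates first from repeat. These are answer combinations, not shares of patients.

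Part of the uncertainty comes from Q2 not saying whether today's infusion counts. If it clearly did not (N = k, or N at least k in the last row), the undetermined cells would fall to k = 1 in the last row for L = 2 (1 of 16) and to k = 1, 2, 3 in the last row for L = 4 (3 of 16). The remainder is due to infusions before the 12-month window, and the result still needs a stated L.

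**Q2 answers.** A first-infusion patient has a true count of 0; Q1 recovers this. A patient first infused long ago, untreated for more than 12 months and now restarting also has a true count of 0, but Q1 reads more than 9 months and does not recover it. Section 8.1.1 expects that some patients stop and restart. A patient with five or more infusions in 12 months has no valid answer either.

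**The case against.** The strongest reply is that the survey already holds a usable split. Q1 identifies first-infusion patients under every assumed course length, and with Q2 it settles 12 of 16 answer combinations at two infusions per course and 10 of 16 at four. The named grouping variable for awareness in section 8.6 is recency of first treatment, which Q1 supplies directly. The course contrast is labelled exploratory. The incident split of off-label use is an addition to the main analysis and is hedged by how accurately incident use can be determined. The questionnaire is a draft, section 8.3 expects changes after testing, and subgroup rules are left to the analysis plan.

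Most of this stands, and it limits the point. A reader might infer that the first-course contrast cannot be formed at all; the documents do not support that, because Q1 and Q2 allow an approximation. A reader might also blame the missing zero in Q2 for the failure of the contrast, and count every first-infusion patient as miscoded: at an assumed 10 to 20% of 500 respondents, that would be 50 to 100 patients. That share is not in the documents, and these are the patients whom Q1 classifies with certainty. The absent course item and definition limit the contrast, not the missing options.

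The reply does not remove the conflict between the two definitions. It also does not supply the missing variable: cognitive pretesting looks for problems with the questions that are asked, and a later analysis plan can work only with what was collected.

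**Conclusion.** The point holds as an inconsistency with a limited effect. Section 8.6 gives 'incident' two meanings. They coincide only if a course is a single infusion, which the protocol does not say. Otherwise the two incident groups differ, and the first-course contrast can be approximated but not reliably formed. The 4 of 16 and 6 of 16 undetermined combinations rest on assumed fixed course lengths of two and four infusions and on Q2 being open about today's infusion. How many patients would fall in those cells cannot be derived from the protocol.

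The gaps in Q2 are a separate, smaller defect. They leave without a valid answer patients who restart after more than 12 months and patients with more than four infusions; first-infusion patients are recovered through Q1.

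It would be wrong to infer that new versus repeat use is a main split for both aims. One use is exploratory and the other secondary. The overall off-label proportion and the main survey percentages are unaffected. The correction is still worth making before fielding, because the missing information cannot be added afterwards.

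**What to change.** Choose one of two routes before the questionnaire is fielded.

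1. Define incident in both components as first infusion versus repeat infusion. The survey takes it from the Q1 answer "This is my first infusion", and the records take it from the first-infusion date on the abstraction form. Reword the exploratory contrast in section 8.6 to match. This needs no new item. The rule must be the same in both places: using Q1's 3-month band in the survey and the 12-month look-back window in the records would again create two definitions.
2. Keep the first-course contrast, define 'course' in the protocol, and add one questionnaire item asking whether today's infusion belongs to the patient's first course. The off-label split then needs either the same definition or a different name.

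Under either route, add 'none before today' and '5 or more' to Q2. The first also makes clear that today's infusion is not counted.

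The cost is one or two sentences in section 8.6 and one or two more response items, with a minor edit to the draft questionnaire and its translations. The planned pretesting can cover the change.

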8.7 DATA MANAGEMENT

A data management plan will be developed to guide the handling of data, including the transfer of electronic files. The data management plan will include, if necessary, country-specific modifications due to local regulations or requirements. The eCRF will be used for both medical record data abstraction and questionnaire completion by patients. The forms will be sent to a data processing centre. Once the forms are received, they will be single-entered into the database. The CRO will follow standard procedures for ensuring accurate data entry, including performing an audit (i.e., a comparison of data on paper to data in the database) of a subset of data entered. Edit and logic checks will be conducted and queries resolved to ensure high-quality data. However, for the patient questionnaire, due to the self-reported nature of the data, some such resolutions may not be possible.

Data managers will conduct UAT of the data entry system and will sign the UAT report before the paper forms are used in the field. Site staff will be trained on data collection forms before the study is fielded. Specialised data managers will approve the data management plan, all annotated data collection forms, data entry system data dictionaries, the data cleaning specifications document, and the testing of summary reports before authorising the data systems to go "live." Data managers will ensure that the paper data systems are tested and valid and will require that testing documentation, database documentation, and change control documentation be created and maintained.

Once the systems are in the field, data management activities will include programming edit checks in preparation for statistical analysis and merging of datasets if required.

Any paper data files collected in the EU will be maintained within the EU. Only deidentified data with case identification numbers will be transferred to the US for data analysis and generation of the final report. Data analysis and storage of de-identified data sets will be in the US. Routine procedures will include checking electronic files, maintaining security and data confidentiality, following analysis plans, and performing quality control (QC) checks of all programs. Each database custodian will maintain any patient-identifying information securely on site according to internal Standard Operating Procedures (SOPs).

Security processes will be in place to ensure the safety of all systems and data. Every effort will be made to ensure that data are kept secure so that they cannot be accessed by anyone except select study staff.

Appropriate data storage and archiving procedures will be followed (i.e., storage on CD-ROM or DVD), with periodic backup of files to tape. Standard procedures will be in place at each research centre to restore electronic files in the event of a hardware or software failure.

8.7.1 Data Quality Assurance

The Sponsor will supply eCRF specifications for this study. The CRO will be responsible for data management of this study, including quality checking of the data. Data entered manually will be collected via Electronic Data Capture (EDC) using eCRFs. Sites will be responsible for data entry into the EDC system. In the event of discrepant data, the CRO will request data clarification from the sites, which the sites will resolve electronically in the EDC system.

The CRO will produce a Data Quality Plan that describes the quality checking to be performed on the data.

The Sponsor will perform oversight of the data management of this study, including approval of the CRO data management plans and specifications. Data will be periodically transferred electronically from the CRO to the Sponsor, and the Sponsor standard procedures will be used to handle and process the electronic transfer of these data.

CRFs and correction documentation will be maintained in the EDC system audit trail. System backups for data stored at the CRO and records retention for the study data will be consistent with the CRO standard procedures.

